8.12 Biomarkers	Language was added that the P2X7 monocyte activation status assay and PBMC inflammatory profile may only be performed in certain countries.	These two assays will not be performed in all countries participating in this study.
1.3 Schedule of Activities; 8.11. Genetics and Pharmacogenomics	The general pharmacogenomics sample will be optional.	It was decided to make this an optional sample.
1.3 Schedule of Activities	UDS was added to each in-person visit.	UDS added to provide additional protection of participant safety and to minimize confounding bias from drug use.
10.7 Appendix 7: Study Conduct During COVID-19	COVID-19 guidance specific to this protocol was added.	Language was added to further clarify protocol specific actions needed to be taken specific to COVID-19.
9.4.1 Primary Endpoints	Primary estimand definition was updated and sensitivity analyses were added. Language was added to further clarify intercurrent events and corresponding handling strategy.	To align with FDA guidance and clarify the strategy for handling intercurrent events.
7.4 Participant Discontinuation/Withdrawal From the Study	Rephrase sentence to remove replacement. Since the additional participants not necessary receive the same intervention as the early withdrawal.	This is a clarification.
1.1 Synopsis Objectives, Overall Design; 1.3 Schedule of activities; 4.1 Overall Design; 4.2 Scientific Rationale for Study Design	The prescreening window has been reduced to up to 3 weeks.	This represents a more realistic timeline to perform the P2RX7 Gain of function (GoF) and Loss of Function (LoF) SNP process.
2.2. Background	It was clarified that in study 55308942EDI1002 that 12 participants were dosed with JNJ-55308942 and/or the tracer [¹⁸F]-JNJ-64413739 .	This is a clarification.
Throughout the protocol	Minor grammatical, formatting, or spelling changes were made.	Minor errors were noted

	Appendix 8 Medications of Special Interest	
	Appendix 9 Conversion of Raw Score to T-Score for PROMIS - Ability to Participate in	
	Social Roles and Activities	38
7 RF	FFFRENCES	39

VERSION HISTORY

Table 1: SAP Version History Summary

SAP Version	Approval Date	Change	Rationale
1.0	21 November 2023	Not Applicable	Initial release
2.0	07 June 2024	1. Section 5.1.2: The end of Week 6 visit window was updated to the day before the first Follow-up/Early Withdrawal visit for safety assessments.	 To clarify the visit window start and end dates. To evaluate the efficacy of JNJ-55308942 compared to placebo on the individual items of the patient-reported
		 Section 5.4.2: Summary statistics and frequency tables were added for individual items of patient-reported outcomes, including PROMIS- Ability to Participate in Social Roles and Activities, PHQ-9, and GAD-7. Section 5.4.2.7: MADRS subgroup analysis by country was added. Section 6.2: The method for handling the assessments that were not performed predose on Treatment Day 1 as per protocol in the analyses was added as a change to protocol planned analyses. Section 6.3: Specifications on the analysis sets to be used for summarizing demographics and baseline characteristics were added. Throughout the SAP: Minor grammatical, formatting, or spelling changes were made. 	outcomes. 3. To evaluate the efficacy of JNJ-55308942 compared to placebo on symptoms of depression in different countries. 4. To utilize all collected data in analyses. A significant change in these assessments is not expected on the same day. 5. To clarify the analysis sets to be used for summarizing demographics and baseline characteristics. 6. Minor errors were noted.

1. INTRODUCTION

This statistical analysis plan (SAP) contains definitions, data handling conventions, algorithms, and statistical methods for the planned analyses for the clinical study report (CSR) of Study 55308942BIP2001 (Protocol Amendment 5, 18 August 2023).

Population pharmacokinetics (PK) and pharmacokinetic/pharmacodynamic (PK/PD) analyses, if conducted, will be specified in separate documents as appropriate.

With the exception of the biomarkers used to define subgroups in the analysis of the secondary endpoints of special interest, analyses of other biomarkers and pharmacogenomics data, if conducted, will be specified in separate documents as appropriate.

1.1. Objectives and Endpoints

Objectives	Endpoints
Primary	
To evaluate the efficacy of JNJ-55308942 compared to placebo on symptoms of depression in participants with bipolar disorders (BD) in a major depressive episode (MDE) at Week 6.	Change in Montgomery-Åsberg Depression Rating Scale (MADRS) total score from baseline at Week 6.
Secondary Objectives of Special Interest	
To evaluate the efficacy of JNJ-55308942 compared to placebo on symptoms of anhedonia.	Change in Snaith-Hamilton Pleasure Scale (SHAPS) total score from baseline at Week 6.
To evaluate the efficacy of JNJ-55308942 compared to placebo on symptoms of depression in participants with BD who are heterozygous or homozygous for the rs P2RX7 Gain of Function (GoF) single-nucleotide polymorphism (SNP) (genetic subgroup analysis)	Change in MADRS total score from baseline at Week 6.
To evaluate the efficacy of JNJ-55308942 compared to placebo on symptoms of depression in participants with BD type I or BD type II (diagnosis subgroup analysis)	Change in MADRS total score from baseline at Week 6.
To evaluate the efficacy of JNJ-55308942 compared to placebo on symptoms of depression in subgroups of patients with specific biomarker profiles (biomarker subgroup analysis).	Change in MADRS total score from baseline at Week 6.

CONFIDENTIAL – FOIA Exemptions Apply in U.S.

Objectives	Endpoints
Secondary	
To evaluate the overall safety and tolerability of treatment with JNJ-55308942 as compared to placebo in participants with symptomatic BD over a treatment period of 6 weeks.	Vital signs (pulse/heart rate [HR], systolic blood pressure [SBP], diastolic blood pressure [DBP], respiratory rate), clinical labs (chemistry, hematology, urinalysis), Adverse Events, ECG, Young Mania Rating Scale (YMRS) score, Columbia Suicide Severity Rating Scale (C-SSRS) score.
To evaluate the effect of JNJ-55308942 compared to placebo on disease severity and improvement on the Clinical Global Impression-Severity scale (CGI-S)	CGI-S
To evaluate the pharmacokinetics (PK) of JNJ-55308942 in participants with BD.	Plasma concentrations of JNJ-55308942.
To assess the effect of JNJ-55308942 on reduction of symptoms associated with depression compared to placebo as measured by self-rated outcomes.	PROMIS – Ability to Participate in Social Roles and Activities, Patient Health Questionnaire-9 (PHQ-9), Generalized Anxiety Disorder 7 (GAD-7) score.
To evaluate the impact of treatment with JNJ-55308942 compared with placebo on response (≥ 50% improvement in MADRS total score from baseline) and remission (MADRS total score ≤12) rates at Week 6.	Response (≥ 50% improvement in MADRS total score from baseline) and remission (MADRS total score ≤12) rates at Week 6.
To evaluate the efficacy of JNJ-55308942 compared to placebo on symptoms of depression in a subgroup of patients with messenger ribonucleic acid (mRNA) transcript levels at baseline that exceed the median level for both P2RX7 and IL-1β.	Change in MADRS total score from baseline at Week 6.
To evaluate the efficacy of JNJ-55308942 compared to placebo on symptoms of depression in subgroups of participants with BD not taking any mood stabilizer or antipsychotic, taking a mood stabilizer alone, taking an antipsychotic alone, and taking a combination of a mood stabilizer and an antipsychotic (concomitant medication subgroup analysis).	Change in MADRS total score from baseline at Week 6.

Objectives	Endpoints
Exploratory	
To explore the pharmacokinetic/pharmacodynamic (PK/PD) relationship between plasma exposure of JNJ-55308942, and efficacy and safety parameters in patients with BD.	Exposure-response between exposure and MADRS and selected safety events, as appropriate.
To explore the effect of JNJ-55308942 on PD-related biomarkers.	Including, but not limited to, blood biomarkers related to immune, inflammatory, hormonal, metabolic, hypothalamic-pituitary-adrenal (HPA) axis, P2X7 receptor and monocyte activity.
To explore the effect of pharmacogenomic variations on the PK, efficacy, and safety of JNJ-55308942.	Influence of genetic polymorphisms (e.g., -1) on plasma exposure, as well as on efficacy and safety measures.
To explore the effect of JNJ-55308942 compared to placebo on the well-being of participants.	Self-Assessment of Well-Being (SAWB) outcome.

1.2. Study Design

[figure not shown]
This is a double-blind, randomized, stratified, placebo-controlled, parallel-group, multicenter study to investigate the efficacy, safety, and tolerability of JNJ-55308942 in bipolar depression. Approximately 164 participants will be enrolled in this study to obtain approximately 132 completers.

The target study population includes participants of any gender, between 18 and 64 years of age inclusive, with a Diagnostic and Statistical Manual of Mental Disorders - 5th edition (DSM-5) diagnosis of BD (types I or II) without current psychotic features as confirmed by the Mini International Neuropsychiatric Interview (MINI) with Borderline Personality Disorder module. The participants should be experiencing an MDE that does not require either hospitalization or antidepressant medication. Each potential participant must satisfy one of the three criteria listed below to meet eligibility for the study population.

- Participants who are currently unmedicated and have not received any mood stabilizers or antipsychotics for four weeks before screening.
- Participants who are on a stable monotherapy regimen of one of the following mood stabilizers (lithium, valproate forms [e.g., divalproex sodium], or lamotrigine) or one of the following antipsychotics (lurasidone, cariprazine, quetiapine, lumateperone, or olanzapine) for four weeks before screening.

• Participants who are on a stable adjunctive regimen of one of the following antipsychotics (lurasidone, quetiapine, lumateperone, or olanzapine) and one of the following mood stabilizers (lithium or valproate forms [e.g., divalproex sodium]) may be considered for eligibility based on the approved therapies in each market with an eligibility assessment conducted between the investigator and sponsor. Assessment of the stable adjunctive regimen of an antipsychotic and a mood stabilizer will be conducted by the investigator and sponsor's clinical judgement and documented for each patient. This regimen must be in place 4 weeks before screening.

The patient must be symptomatic as assessed using the 17-item Hamilton Depression Rating Scale (HDRS17). Symptom intensity over the past week will be evaluated.

Participants who are enrolled in the study will continue on their current medication regimen, if applicable, throughout the study. No dose changes are permitted from screening through the end of the study (until after the follow-up visit). No concurrent use of antidepressants will be allowed until after the follow-up visit.

For each participant, the study will consist of 3 phases: a screening phase of up to 4 weeks, a double-blind treatment phase of 6 weeks, and a post-treatment follow-up phase of up to 2 weeks (Figure 1). After giving written informed consent for screening, participants will be screened between 28 days and 1 day before the double-blind treatment phase to ascertain their eligibility for the study according to the inclusion and exclusion criteria. Eligible participants will enter the double-blind treatment phase where they will be randomly assigned with a 1:1 ratio to once daily administration with mg JNJ-55308942 or placebo for 6 weeks, Day 1 up to and including the last treatment visit, Day 43 +/- 1 day. Between approximately 1 to 2 weeks after administration of the last dose, participants will return to the study site for a follow-up visit. The total study duration for each participant will be up to 12 weeks. There will be 7 scheduled visits to the study site during the study, including screening and follow-up visit.

Treatment Period Follow-up Visit Screening (Efficacy/Safety) **Study complete** Up to 4 weeks Double-blind, 6 weeks BD type I and II in a current MDE All participants 1-2 weeks **Include GoF P2X7 mutation** Placebo Exclude complete LoF P2X7 mutations JNJ-55308942 Up to 4 weeks 6 weeks At 6 weeks: **Primary endpoint MADRS**

Figure 1: Schematic Overview of the Study

1.2.1. Randomization and Blinding

Procedures for Randomization

Central randomization will be implemented in this study. Participants will be randomly assigned to 1 of 2 groups (JNJ-55308942 or placebo) based on a computer-generated randomization schedule prepared before the study by or under the supervision of the sponsor. The randomization will be balanced by using randomly permuted blocks and will be stratified by 4 factors: BD type (I or II), country, P2RX7 GoF SNP mutation genotype (homozygous or heterozygous), as well as concomitant medication status (no mood stabilizer or antipsychotic, a mood stabilizer alone, an antipsychotic alone, or a combination of a mood stabilizer and an antipsychotic). The interactive web response system (IWRS) will assign a unique intervention code, which will dictate the intervention assignment and matching study intervention kit for the participant.

Blinding

Blinded treatment will be used to reduce potential bias during data collection and evaluation of clinical endpoints.

The investigator will not be provided with randomization codes. The codes will be maintained within the IWRS, which has the functionality to allow the investigator to break the blind for an individual participant.

Data that may potentially unblind the intervention assignment (e.g., study intervention plasma concentrations, plasma biomarkers) will be handled with special care to ensure that the integrity of the blind is maintained and the potential for bias is minimized. This can include making special provisions, such as segregating the data in question from view by the investigators, clinical team,

or others as appropriate until the time of database lock and unblinding. Also, the site staff should not discuss insights on unblinding of randomization with the participants.

Under normal circumstances, the blind should not be broken until all participants have completed the study and the database is finalized/locked. The investigator may, in an emergency, determine the identity of the intervention by contacting the IWRS. While the responsibility to break the intervention code in emergency situations resides solely with the investigator, it is recommended that the investigator contact the sponsor or its designee if possible, to discuss the particular situation, before breaking the blind.

Participants who have had their study intervention assignment unblinded should continue to return for scheduled evaluations.

In general, randomization codes will be disclosed fully only if the study is completed and the clinical database is closed/locked.

2. STATISTICAL HYPOTHESES

The primary objective of this study is to evaluate the efficacy of JNJ-55308942 compared to placebo on symptoms of depression in participants with BD in an MDE. The null hypothesis that will be tested to address the primary objective of the study is that there is no difference between JNJ-55308942 (Image once daily) and placebo in reducing the symptoms of depression in participants with BD in an MDE as assessed by change in MADRS total score from baseline to Week 6.

3. SAMPLE SIZE DETERMINATION

The estimated sample size of 164 participants (82 participants per group) was determined based on the assumption of an effect size of at least 0.45 for the MADRS total score (difference in mean change from baseline at Week 6 between the JNJ-55308942 and placebo groups of 3.9 units with a standard deviation of 8.6). This is considered to be a clinically relevant difference in a population with BD types I and II. The standard deviation of 8.6 in the change in MADRS total score from baseline is a reasonable assumption based on data in a published phase 3 study of quetiapine in BD type I and type II depression (Calabrese 2005). Power is set at 90%, with a 1-sided alpha of 0.10 and a 6-week drop-out rate of 20%. The estimated number of completers to be included in the primary analysis is 132.

4. POPULATIONS (ANALYSIS SETS) FOR ANALYSIS

Population	Description
Enrolled	All participants who signed the ICF at screening
Randomized	All participants who were randomized in the study
Full Analysis Set (FAS)	All randomized participants who received at least 1 dose of study
	intervention and have both the baseline and at least 1 post-
	baseline MADRS measurement
Safety	All randomized participants who take at least 1 dose of study
	intervention
Pharmacokinetics (PK)	All participants who received at least 1 dose of JNJ-55308942
Analysis Set	and have at least 1 valid blood sample drawn for PK analysis

The randomized analysis set will be used for summarizing the overall study completion/withdrawal information. Efficacy analyses will be based on the full analysis set unless otherwise specified. Safety analyses will be based on the safety analysis set and PK analyses will be based on the PK analysis set.

5. STATISTICAL ANALYSES

5.1. General Considerations

Continuous variables will be summarized by descriptive statistics including the number of participants (N), mean, standard deviation (SD), median, and range (minimum; maximum) unless otherwise specified. Categorical variables will be summarized by frequency counts and percentages.

5.1.1. Analysis Phases

Screening

The screening phase begins on the date the first informed consent is obtained and ends 1 day before the first dose of study intervention in the double-blind treatment phase. The screening phase end date is left missing for those participants who did not receive study intervention.

Double-Blind Analysis Phase

The analysis reference start date of the double-blind analysis phase is the date of the first dose of the double-blind study intervention. The analysis reference end date of the double-blind analysis phase is the date of study disposition (last contact).

5.1.2. Visit Windows

As participants do not always adhere to the protocol visit schedule, the following rules are applied to assign actual visits to analysis visits. Listed below are the visit windows and the target days for each visit. The reference day is Study Day 1 (which is the first day the study drug was taken in the double-blind treatment phase). If a subject has 2 or more actual visits in one visit window, the visit closest to the target day will be used as the protocol visit for that visit window. The other additional

visit(s) will not be used in the summaries or analyses. If 2 actual visits are equidistant from the target day within a visit window, the later visit is used.

All assignments will be made in chronological order. Once a visit date is assigned to a visit window, it will no longer be used for a later time point except for the endpoint. Listed below (Table 2) are the analysis visit windows and the target days for each visit defined in the protocol.

The baseline is defined as the last observation before the start of the first study intervention administration in the double-blind treatment phase. Assessments prior to Day 1 of the double-blind treatment phase that are not considered baseline assessments will be labeled as 'Screening'.

Table 2: Visit Windows

			Time Interval		
	Analysis	Scheduled	(Label on	Time Interval	Target Time
Parameter	Phase	Visit Number	Output)	(Day)*	Point (Day)*
MADRS,	Double-Blind	2	Baseline	≤1	1
CGI-S		3	Week 1	[2,11]	8
		4	Week 2	[12,21]	15
		5	Week 4	[22,35]	29
		6	Week 6	≥36	43
SHAPS	Double-Blind	2	Baseline	≤1	1
		6	Week 6	≥2	43
PROMIS, PHQ-9	Double-Blind	2	Baseline	≤1	1
, ,		3	Week 1	[2,11]	8
		4	Week 2	[12,18]	15
			Week 3	[19,25]	22
		5	Week 4	[26,32]	29
			Week 5	[33,39]	36
		6	Week 6	≥40	43
GAD-7	Double-Blind	2	Baseline	≤1	1
		4	Week 2	[2,21]	15
		5	Week 4	[22,35]	29
		6	Week 6	≥36	43
Clinical	Screening	1	Screening	<1	<1
Laboratory tests	Double-Blind	2	Baseline	≤1	1
(Hematology,		4	Week 2	[2,21]	15
Serum, Urinalysis)		5	Week 4	[22,35]	29
		6	Week 6	[36, Day of FU/EW)	43
		7	FU/EW		49 to 56
Vital signs,	Screening	1	Screening	<1	<1
12-lead ECG,	Double-Blind	2	Baseline	≤1	1
C-SSRS,		3	Week 1	[2,11]	8
Urine Drug Screen		4	Week 2	[12,21]	15
		5	Week 4	[22,35]	29
		6	Week 6	[36, Day of FU/EW)	43
		7	FU/EW		49 to 56
Physical	Screening	1	Screening	<1	<1
examination,	Double-Blind	2	Baseline	≤1	1
Body weight		6	Week 6	[2, Day of FU/EW)	43
		7	FU/EW		49 to 56
YMRS	Screening	1	Screening	<1	<1
	Double-Blind	2	Baseline	≤1	1
		3	Week 1	[2,11]	8

CONFIDENTIAL – FOIA Exemptions Apply in U.S.

12

Table 2: Visit Windows

Parameter	Analysis Phase	Scheduled Visit Number	Time Interval (Label on Output)	Time Interval (Day)*	Target Time Point (Day)*
		4	Week 2	[12,21]	15
		5	Week 4	[22,35]	29
		6	Week 6	≥36	43

^{*}Relative to Study Day 1; FU/EW = Follow-up/Early Withdrawal

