5.6.3.3. Electrocardiogram

The ECG parameters that will be analyzed are heart rate (HR), PR interval, QRS interval, QT interval, and corrected QT(QTc) interval using the following correction methods: Bazett's formula (QTcB), and Fridericia's formula (QTcF).

Bazett's formula: QTcB (msec) = QT (msec) * $(HR(bpm)/60)^{0.5}$;

Fridericia's formula: QTcF (msec) = QT (msec) * $(HR(bpm)/60)^{0.33}$

If ECG measurements are repeated at a visit, they will be averaged. The averaged value will considered the 'Visit' ECG result.

Descriptive statistics of ECG parameters and change from baseline will be summarized at each scheduled time point by intervention group.

The number and percentage of participants with categorized QTc interval values will be summarized at each scheduled time point. The number and percentage of participants with categorized QTc interval increases from baseline to the maximum postbaseline value will be summarized. A shift table will be provided summarizing the shift from baseline to maximum QTc interval classification. Refer to Table 5 for summary categories.

Table 5: Criteria for Abnormal QTc Values and Changes from Baseline

QTc value (msec)	Normal QTc	nal QTc ≤450 for male, ≤470 for female	
		>450 to ≤480 for male, >470 to ≤480 for female	
		>480 to \(\leq 500\)	
		>500	
QTc change from baseline (msec)	No concern	≤30	
	Concern	>30 to ≤60	
	Clear concern	>60	

Abnormality criteria (Table 6) will be applied to baseline and postbaseline values. Postbaseline abnormalities will be compared with their corresponding baseline result:

- Treatment-emergent will be concluded if the postbaseline value is above the upper limit and the baseline value is below the upper limit (e.g., Normal or Low). The same applies to the postbaseline value being below the lower limit with the baseline value being above the lower limit (e.g., Normal or High).
- If the baseline value is missing, a postbaseline abnormality will always be considered as treatment-emergent.

The number and percentage of participants with treatment-emergent abnormal postbaseline values (relative to baseline) will be presented by intervention group over time:

ECG Parameter	Abnormally low	Abnormally high
Heart Rate (bpm)	<50 bpm	>100 bpm
PR interval (msec)	<120 msec	>200 msec
QRS interval (msec)	<60 msec	>120 msec
QT interval (msec)	<200 msec	>500 msec

Table 6: Abnormal Limits for ECG Parameters

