5.6.3.4.2. Columbia Suicide Severity Rating Scale (C-SSRS)

The C-SSRS is a low-burden measure of the spectrum of suicidal ideation and behavior that was developed to assess severity and track suicidal events through any intervention (Posner 2007). It is a clinical interview providing a summary of both suicidal ideation and behavior that can be

administered during any evaluation or risk assessment to identify the level and type of suicidality present. The C-SSRS has been used frequently in clinical studies and is a validated, standard measure for suicidal ideation assessment. Using the C-SSRS, the outcomes will be categorized using the scoring for the 11 categories:

Suicid	Suicidal Ideation (1-5)		
1	Wish to be dead		
2	Non-specific active suicidal thoughts		
3	Active suicidal ideation with any methods (not plan) without intent to act		
4	Active suicidal ideation with some intent to act, without specific plan		
5	Active suicidal ideation with specific plan and intent		
Suicid	Suicidal Behavior (6-10)		
6	Preparatory acts or behavior		
7	Aborted attempt		
8	Interrupted attempt		
9	Actual attempt		
10	Suicide		
Non-s	Non-suicidal self-injurious behavior (11)		
11	Non-suicidal self-injurious behavior		

If no events qualify for a score of 1 to 10, a score of 0 will be assigned (0 = "no suicidal ideation or behavior that can be assessed on the basis of C-SSRS"). A participant with a score of 11 will be considered as not having suicidal ideation or behavior.

Shifts from baseline to the maximum postbaseline score pertaining to suicidal ideation or suicidal behavior (i.e., scores 1 to 10) will be summarized by intervention group.

The maximum score (of scores 1 to 10) assigned to each participant will be grouped into one of three broad categories: No suicidal ideation or behavior (0), Suicidal ideation (1-5), and Suicidal behavior (6-10). Shifts from baseline to the maximum postbaseline category will be summarized by intervention group.

Frequency distribution of the scores for the 11 categories will be provided at each time point by intervention group.

A listing of C-SSRS items throughout the study for participants with Suicidal Ideation or Behavior at any time point will be provided.

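### SAP 5.1.2 sets aside non-selected visits and states no exception for the maximum-postbaseline QTc and C-SSRS tables, so a literal reading can make those maxima too low

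*SAP*

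**What the plan says.** SAP 5.1.2 introduces its windowing with the words "the following rules are applied to assign actual visits to analysis visits". If a participant has several visits in one window, the visit nearest the target day is kept, and the later one in a tie. The additional "visit(s) will not be used in the summaries or analyses". The section's only exception lets an assigned visit be used again for the endpoint; it does not bring back a visit that was not selected.

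Table 2 lists 12-lead ECG and C-SSRS by name. Their postbaseline windows are Week 1 [2,11], Week 2 [12,21], Week 4 [22,35] and Week 6 [36, day of follow-up/early withdrawal), with target days 8, 15, 29 and 43. The follow-up/early withdrawal visit has its own row.

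Two sections then use worst values:

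- **QTc, SAP 5.6.3.3.** By visit, "categorized QTc interval values will be summarized at each scheduled time point". For the worst value, categorized QTc "increases from baseline to the maximum postbaseline value will be summarized", and "A shift table will be provided summarizing the shift from baseline to maximum QTc interval classification". On repeats: "If ECG measurements are repeated at a visit, they will be averaged".
- **C-SSRS, SAP 5.6.3.4.2.** "Shifts from baseline to the maximum postbaseline score pertaining to suicidal ideation or suicidal" behavior are summarized by arm, and again with the scores grouped as 0, 1-5 and 6-10. Separately, a listing of C-SSRS items for "participants with Suicidal Ideation or Behavior at any time point will be provided".

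Neither section, nor the list of changes to planned analyses in SAP Appendix 2, says whether unscheduled or non-selected visits count towards a maximum.

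**The concern.** A nearest-to-target rule suits a by-visit summary, where each participant should contribute one value per time point. It does not suit a worst-value table, whose purpose is to catch the extreme reading whenever it occurred. Because the exclusion in SAP 5.1.2 is worded for summaries and analyses in general, a programmer who follows it literally would take the maximum over the selected visits only.

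Off-schedule records can arise. SAP 5.1.2 itself expects departures from the schedule. Protocol 10.7.2 has assessments done outside a scheduled visit entered as unscheduled visits. Protocol 8.7.3 obliges the investigator to make supplemental measurements for an adverse event where medically indicated, and Protocol 8.6.3 has clinically relevant ECG abnormalities recorded as adverse events. None of these provisions specifically calls for an unscheduled ECG or C-SSRS, so the route is plausible but inferred. At stake are the by-arm tables of worst QTc and worst C-SSRS result. No efficacy result is touched.

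**Working it through.** The plan states no figure on this point, so there is none to reproduce. The check applies the SAP 5.1.2 rule to the Table 2 windows. All QTc and C-SSRS values below are invented for illustration.

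**1. Do scheduled visits collide?** With the ±1 day allowance, visits fall on Days 7-9, 14-16, 28-30 and 42-44. These lie in [2,11], [12,21], [22,35] and the Week 6 window respectively, one visit to a window. Nothing is dropped, and the two readings give the same maximum. The issue needs a second visit in the same window.

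**2. QTc, boundary crossed.** Change from baseline: +20 msec on Day 29, +62 msec at an unscheduled Day 33 visit, +25 msec on Day 43.

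- Days 29 and 33 both lie in [22,35], target 29. Distances: |29 − 29| = 0 and |33 − 29| = 4, so Day 33 is not selected.
- All records: max(20, 62, 25) = 62, in the above-60 class of SAP Table 5.
- Selected visits only: max(20, 25) = 25, in the 30-or-below class.

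**3. QTc, boundary not crossed.** Replace the Day 33 value by +28 msec. All records give max(20, 28, 25) = 28; selected visits give 25. Both are 30 or below, so the table does not change.

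**4. C-SSRS.** Scores: 1 on Day 8, 0 on Day 15, 4 at an unscheduled Day 24 visit, 1 on Day 29, 0 on Day 43.

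- Days 24 and 29 share [22,35]. Distances are 5 and 0, so Day 24 is not selected.
- All records: maximum 4. Selected visits only: maximum 1.
- The individual-score shift changes. The broad category does not, because 4 and 1 both lie in 1-5.

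**5. Direction.** The maximum of a subset cannot exceed the maximum of the full set, so the literal rule leaves the table value unchanged or lowers it.

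**6. Unit effect.** With the 82 participants per arm in SAP Section 3 as denominator, one participant moved across a category boundary changes that arm's percentage by 1/82 = 1.2 percentage points. The documents give no frequency of off-schedule ECGs or C-SSRS, so this cannot be scaled up to an expected total.

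**The case against.** The strongest reply is that SAP 5.1.2 only maps visits: it opens as a way of assigning actual visits to analysis visits, and it selects the record that stands for each window. SAP 5.6.3.3 separates results at scheduled time points from the maximum and puts no visit limit on the maximum. SAP 5.6.3.4.2 draws the same distinction. A specific derivation normally governs a general convention. Other parts of the SAP also suggest that no purge of records was meant: the hepatic listing in 5.6.3.1 depends on repeat testing, which will often share a window with the first test, and the YMRS and C-SSRS listings run across the whole study.

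This reading is plausible, but no sentence in the SAP adopts it. The supporting examples are listings, and for C-SSRS the any-time-point wording appears only there. SAP version 2.0 also revised the Week 6 window specifically for safety assessments, so applying windows to safety data was deliberate.

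Three further limits stand:

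- **C-SSRS route.** Protocol 7.4 says participants with acute suicidal ideation judged clinically meaningful should be withdrawn. If withdrawal follows an off-schedule assessment, no later scheduled visit may exist to displace it, and the follow-up/early withdrawal visit is kept. The C-SSRS example above may therefore not fit practice for a serious score. This narrows the C-SSRS half but does not exclude every case.
- **ECG repeats.** Those taken at one visit are averaged and are not affected.
- **Other outputs.** Adverse event tables and listings, including the listing of clinically relevant ECG abnormalities, may still show the event. They do not correct the by-arm maximum tables.

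**Conclusion.** The concern holds as a minor one. The SAP has an unqualified exclusion that covers ECG and C-SSRS, and its maximum tables name no source visits. Two programmers could follow it in good faith and produce different worst-value tables. Any error is in one direction: equal or too low.

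A reader might infer more than the documents support:

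- That the SAP definitely discards worst values. It does so only on the literal reading, and only when two or more visits share a window.
- That every excluded maximum changes a reported percentage. For the QTc tables and the broad C-SSRS categories this requires crossing a category boundary. Only the individual-score C-SSRS shift changes whenever the maximum differs.
- That a total understatement can be estimated. Any range would rest on an assumed count of affected participants, for which the documents give no basis.

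The size that can be stated is 1.2 percentage points per participant who crosses a boundary, assuming the planned 82 per arm as denominator.

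**What to change.** In SAP 5.1.2, limit the nearest-to-target rule to by-visit summaries and the efficacy models. In SAP 5.6.3.3 and 5.6.3.4.2, state that the maximum-postbaseline QTc and C-SSRS derivations use all postbaseline assessments, including unscheduled and non-selected ones, with ECGs repeated at one visit averaged first.

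This is a cheap improvement: two or three sentences, a little extra programming and no new data. The one downside for the sponsor is that worst-value safety figures may look slightly less favourable.
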